### **STUDY DESIGN**

The study is a multi-center, prospective, randomized study comparing surgical and economic parameters of Total Knee Replacement performed with single-use Efficiency instruments with patient-specific technique (MyKnee®) versus traditional metal instruments with conventional surgical technique. The objective is to evaluate the impact of single-use instrumentation versus traditional metal instruments in reducing overall surgical costs and improving mechanical axis alignment. The timing of routine surgical phases will be measured, including the pre-operative preparation time, intra-operative phase, OR clean-up time and sterilization phase in 300 adult patients undergoing total knee replacement. AP and lateral x-rays will be utilized to assess the implant's mechanical axis alignment and tibial slope after discharge to the completion of the 6 week visit. Additionally, other parameters will be recorded including blood loss, post-op day 1 hemoglobin drop, adverse events, number of trays sent to sterilization, and total waste weight at the end of each procedure, considering separately those recyclable and those not recyclable. To ensure that the minimum of 300 patients is met, 342 patients will be randomized into two treatment cohorts in a 2:1 ratio.

#### **Group A: Single-Use Efficiency Instruments with Patient Specific Technique (Efficiency/MyKnee®)**

Patients randomized to Group A will undergo surgery utilizing single-use Efficiency Instruments with patient-specific technique (MyKnee® patient-matched cutting blocks)

#### **Group B: Traditional Metal Instruments with Conventional Surgical Technique (Conventional TKA)**

Patients randomized to Group B will undergo conventional surgical technique utilizing traditional metal instrumentation and traditional cutting blocks (Metal)

Additional demographic information will be collected to describe the study population and to document whether the two treatment groups are clinically comparable. Data collected will include: age, gender, BMI, race/ethnicity, smoking history, and employment status, in addition to pre-operative knee history/diagnosis and degree of pre-operative knee malalignment and Kellgren-Lawrence grade.

## 3

### **PATIENT RECRUITMENT AND SAMPLE**

#### **SIZE**

The study participants will be recruited from the patients receiving care with one of the study investigators or their practice partners. Participating clinicians and their staff will be notified of this protocol and will be asked to refer patients undergoing total knee arthroplasty.

342 patients will be enrolled and randomized with 2:1 ratio, MyKnee/Efficiency (n = 228) : Conventional/Metal (n = 114).

#### **3.1 Inclusion/Exclusion Criteria**

All inclusion and exclusion criteria will be reviewed by the investigator or qualified designee to ensure that the subject qualifies for the study prior to enrollment and randomization. Subjects must meet all inclusion criteria and none of the exclusion criteria to be eligible for the study.

### 3.1.1

#### **Inclusion Criteria**

In order to be eligible for participation in this study, the patient must meet all of the following inclusion criteria:

- 1) Age 18 to 75 years
- 2) BMI  $\leq 40$
- 3) Undergoing unilateral total knee arthroplasty due to osteoarthritis (primary or post-traumatic OA)
- 4) Able and willing to give consent and to comply with study requirements, including follow up visit at 6 weeks

### 3.1.2

#### **Exclusion Criteria**

The subject must be excluded from participating in the study if the subject meets any of the following exclusion criteria:

- 1) Pregnant women or those seeking to become pregnant. Pregnancy test is administered prior to surgery as part of routine care by the hospital / surgery center for all female patients of childbearing potential
- 2) Is participating in another clinical study
- 3) Has inflammatory arthritis
- 4) Has knee avascular necrosis
- 5) Has severe deformity, defined as greater than 15 degrees varus or valgus relative to the mechanical axis.
- 6) Has retained hardware in the knee that requires removal or interferes with TKA procedure

## **3.2 Study Procedures**

Patients who are undergoing a unilateral total knee arthroplasty and meet all of the inclusion/exclusion criteria will be approached to participate in the study. If consent is obtained the study coordinator will be notified. The coordinator will randomize the patients in a 2:1 ratio to one of the two treatment cohorts (i.e., total knee arthroplasty utilizing Efficiency instruments with patient specific technique (MyKnee®) or total knee arthroplasty with traditional metal instruments with conventional surgical technique respectively).

Preoperatively, subjects randomized to Group A (Efficiency/MyKnee®) will undergo a pre-operative CT scan or MRI as standard of care. The investigator will perform appropriate pre-operative planning which enables the custom manufacturing of the MyKnee® cutting blocks that will be delivered to the surgical facility. Subjects randomized to Group B (Conventional TKA) will undergo imaging required for preoperative planning as deemed standard of care by the investigator.

At the next visit all subjects will undergo the total knee arthroplasty procedure utilizing the assigned instrumentation. Timing of various operative and sterilization phases will be recorded. Following the procedure, the patient will undergo X-rays after discharge to the completion of the 6 week visit to examine the alignment of the implant.

### 3.2.1

#### **Informed Consent**

Individuals who agree to participate in this study will be asked to provide formal written informed consent. A signed copy of the informed consent form will be given to the patient, and the original will be maintained in the patient file.

Consent must be documented by the subject's dated signature or by the subject's legally acceptable representative's dated signature on a consent form along with the dated signature of the person conducting the consent discussion.

The initial informed consent form, any subsequent revised written informed consent form and any written information provided to the subject must receive the IRB/EC's approval/favorable opinion in advance of use. The subject or his/her legally acceptable representative should be informed in a timely manner if new information becomes available that may be relevant to the subject's participation in the study. The communication of this information will be provided and documented via a revised consent form or addendum to the original consent form that captures the subject's dated signature or by the subject's legally acceptable representative's dated signature.

### 3.2.2

#### **Randomization**

Patients will be randomized using a computer generated blocked randomization with 2:1 allocations to the single-use Efficiency instruments (and MyKnee) versus traditional metal instruments (conventional TKA) groups. The randomization will be performed separately for each site.

In case the investigator decides not to include the patient after randomization, this patient will be treated as withdrawn although a randomization has been performed. The reason for withdrawal must be documented in the patient file. The used randomization number cannot be used again. For the next patient, the following randomization number will be used.

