#### **Secondary Objectives:**

To compare the following surgical and clinical outcomes between the two study groups

- To compare correction of alignment after total knee replacement via long standing AP hip-knee-ankle x-rays.
- To compare the accuracy of tibial slope angle on a lateral knee x-ray
- To compare the number of trays sent to sterilization
- To compare the volume of estimated blood loss during the procedure
- To compare the drop in post-operative (day 1) hemoglobin and total volume of transfusions (allogeneic and/or autologous)
- To compare the occurrence of adverse events
- To compare the waste weight at the end of each surgery, considering separately those recyclable and those not recyclable.
- To compare the rate of intraoperative and post-operative complications
- To compare the rate of successful use of MyKnee® cutting blocks (i.e. the incidence of surgical cases where the surgeon did not need to abort the use of MyKnee intra-operatively and default to the use of standard cutting blocks).

The cost-per-minute value based on hospital estimates will be used to calculate an overall cost-savings total.

## 2

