#### **4.1 Data Analysis**

The objectives of this study are outlined in Section 1.3. For purposes of this study, economic outcomes of interest include the peri-operative time, intra-operative time (OR efficiency), and sterilization times as quantitative values. These outcomes will be subsequently used in comparative cost analyses. The secondary objectives are to assess the accuracy of mechanical axis alignment and posterior tibial slope after total knee replacement, additional operative parameters, and adverse events.

Descriptive statistics, specifically means will be used to summarize the peri-operative, intra-operative and sterilization time data.

The primary objective will be met by comparing mean values of each of the time-saving parameters. The null hypotheses of no differences in mean values between re-usable and single-use devices will be tested using separate t-tests for two independent groups for each endpoint. A p-value of less than 0.05 will be considered significant for each endpoint. Endpoints with statistically significant differences are expected to contribute to expected cost differences to be determined in subsequent analyses.

Descriptive analyses as well as similar two-sample comparisons will be used to evaluate secondary measures.

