#### **4.2 Sample Size Analysis**

Sample size for this study was determined on the basis of device group differences observed in the Mont et al 2013 study for four (related) but important health care utilization endpoints. The table below summarizes the data in Table 2 of Mont et al, but also provides a summary of the comparisons between single-use and re-usable pooling over whether or not navigation was employed. These data were used to approximate the expected effect size (standardized mean difference) comparing between single-use vs re-useable instruments. The sample sizes required for a two sample t-test to obtain 80%, 85%, and 90% power as a function of the observed pooled effect sizes were determined. The effect sizes were derived from the reported mean differences and p-values. The maximum sample size per group required to achieve at least 80% statistical power to reject the null hypothesis of equal group mean was determined across the four outcomes summarized in Table 2. For the 2:1 allocation between the single-use Efficiency instruments with MyKnee versus traditional metal instruments, this sample size was 200:100 or total N=300. This value was increased by 14% to N=342 to account for uncertainty in the estimated effect sizes, to account and to allow for additional analyses of economic outcomes. Therefore, 228 and 114 patients will be randomly allocated into single-use Efficiency instruments and traditional metal instruments arms respectively.

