### Sample Size Analysis for Main Effect of Traditional vs Single-Use Devices

Outcome	Instrument	Traditional		Single-Use		Mean Difference (d)	p-value	SD from means and p-value	Analysis			
		Nevi.	patients	Mean	patients				Effect Size = d/SD	N total 2:1 (80%)	N total 2:1 (85%)	N total 2:1 (90%)
Instrument Set-up Time	No	96	36.61	95	33.56	3.050	0.002	6.82	0.447	300	340	400
	Yes	97	39.00	100	35.96	3.040	0.042	10.49	0.290			
	Comb.	193	37.42	195	34.43	2.985		8.66	0.345			
Instrument Cleanup	No	96	16.43	95	13.59	2.840	0.001	5.96	0.476	240	275	320
	Yes	97	24.96	100	20.09	4.870	0.011	13.44	0.362			
	Comb.	193	20.50	195	16.75	3.752		9.72	0.386			
Combined	No	96	53.04	95	47.15	5.890	0.001	12.37	0.476	180	195	225
	Yes	97	63.96	100	56.05	7.910	0.001	16.87	0.469			
	Comb.	193	57.92	195	51.18	6.737		14.63	0.460			
Surgical Episode Time	No	96	100.58	95	97.11	3.470	0.100	14.58	0.238	290	330	385
	Yes	97	128.51	100	119.61	8.900	0.001	18.98	0.469			
	Comb.	193	113.43	195	107.54	5.893		16.79	0.351			

## 5

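### Site is a randomization stratum but is missing from the analysis; adding it with robust standard errors would improve precision at almost no cost

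*Combined protocol and SAP*

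**What the plan says.** Section 3.2.2 (Randomization) specifies "computer generated blocked randomization with 2:1 allocations" and adds: "The randomization will be performed separately for each site". Site is therefore a stratum of the design.

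Section 4.1 (Data Analysis) says that the null hypotheses for the time endpoints "will be tested using separate t-tests for two independent groups for each endpoint", and that "A p-value of less than 0.05 will be considered significant for each endpoint". For the rest: "Descriptive analyses as well as similar two-sample comparisons will be used to evaluate secondary measures". It does not say whether the t-test pools the variances or is a Welch test.

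Section 4.2 (Sample Size Analysis) sizes the trial on a two-sample t-test, arrives at 200:100, and then states: "This value was increased by 14% to N=342 to account for uncertainty in the estimated effect sizes". The stated reasons for the margin also include further economic analyses.

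Nowhere in section 4 is site a covariate, a stratum or a random effect. The documents give neither the number of sites nor a between-site variance, and they do not show whether the planning SDs are within-site or total.

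**The concern.** Blocking within site removes between-site variation from the treatment contrast. A t-test that ignores site still counts that variation in its standard error. If site means differ and the arms have similar within-site variances (or a Welch test is used), the intervals are too wide and the test is conservative. Several endpoints in section 3.3, such as transport to the sterilization unit, cleaning and return to stock, plausibly depend on the facility, so site differences are likely.

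The conservative direction is not guaranteed. With a pooled variance, 2:1 allocation and a more variable metal arm, which is the smaller one, the standard error can be too small instead.

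Section 4.1 judges each endpoint at p < 0.05 and passes significant endpoints on to the cost analysis. The real error rate and power of that rule would therefore depend on site spread and arm variances that the planned test does not handle.

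The point covers comparisons between arms only. The cutting-block success rate in the secondary objectives ("the incidence of surgical cases where the surgeon did not need to abort the use of MyKnee intra-operatively") exists only in Group A, so no comparison between arms applies to it.

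**Working it through.** **Inputs.** From the section 4.2 table, "Sample Size Analysis for Main Effect of Traditional vs Single-Use Devices", the combined row for instrument set-up time gives a mean difference of 2.985, an SD of 8.66 and an effect size of 0.345. From the section 4.2 text: 200:100 (N=300), raised to 228:114 (N=342), with a target of 80% power. Alpha is 0.05, taken as two-sided. The site share of total variance, s, is an assumption shown at 5%, 10%, 20% and 30%.

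**1. The plan's own figure.** The size of the smaller arm is 1.5 × (1.960 + 0.842)² / 0.345² = 98.9, so 99, and the total is 297. The exact t calculation gives 300, as stated. 300 × 1.14 = 342. The planned N reproduces.

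**2. Noncentrality.** d = 2.985/8.66 = 0.345.
- N=342: d × √(228 × 114/342) = 3.005; power Φ(3.005 − 1.96) = 85.2%.
- N=300: d × √(200 × 100/300) = 2.814; power Φ(2.814 − 1.96) = 80.4%.

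**3. Equal arm variances.** The unadjusted standard error is too large by k = 1/√(1 − s).
- Type I error = 2Φ(−1.96k).
- Case (a), 8.66 is a within-site SD: unadjusted power Φ(ncp − 1.96k), adjusted Φ(ncp − 1.96).
- Case (b), 8.66 is a total SD: unadjusted power Φ(k(ncp − 1.96)), adjusted Φ(k × ncp − 1.96).

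| Site share | k | Type I error | (a) unadj. / adj., N=342 | (b) unadj. / adj., N=342 | (a) unadj. / adj., N=300 |
|---|---|---|---|---|---|
| 5% | 1.026 | 4.4% | 84.0 / 85.2% | 85.8 / 86.9% | 78.9 / 80.4% |
| 10% | 1.054 | 3.9% | 82.6 / 85.2% | 86.5 / 88.6% | 77.3 / 80.4% |
| 20% | 1.118 | 2.8% | 79.2 / 85.2% | 87.9 / 91.9% | 73.3 / 80.4% |
| 30% | 1.195 | 1.9% | 74.6 / 85.2% | 89.4 / 94.9% | 68.1 / 80.4% |

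In case (a) at N=342, unadjusted power reaches 80% when 3.005 − 1.96k = 0.842. That gives k = 1.104 and s = 1 − 1/k² = 0.179.

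**4. Unequal arm variances.** Set the single-use within-site SD to 1 and the metal SD to r (an assumption; the documents give no SDs by arm).
- w = (227 + 113r²)/340; site variance = w × s/(1 − s).
- True variance of the difference: T = 1/228 + r²/114.
- Pooled estimate: E = (w + site variance) × (1/228 + 1/114).
- Type I error = 2Φ(−1.96 × √(E/T)). For Welch, E = T + site variance × (1/228 + 1/114).

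At r = 1.25, w = 1.187 and T = 0.01809. With s = 0, E = 0.01562 and pooled type I error is 6.9%.

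| Site share | Pooled, metal SD 25% larger | Welch, metal SD 25% larger | Pooled, single-use SD 25% larger |
|---|---|---|---|
| 0% | 6.9% | 5.0% | 3.5% |
| 5% | 6.2% | 4.5% | 3.0% |
| 10% | 5.5% | 4.0% | 2.6% |
| 20% | 4.2% | 3.1% | 1.8% |
| 30% | 3.0% | 2.2% | 1.2% |

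The pooled test crosses 5% at a share of 0.137 for r = 1.25 and 0.228 for r = 1.5.

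**5. Simulation.** 3,000 null trials per setting; 3 or 10 sites of about equal size and blocks of 6 were assumed; Monte Carlo error is about 0.4 points.
- Equal variances, pooled t-test: 3.4–3.7% at a 10% share and 1.8–1.9% at 30%.
- Metal SD 25% larger, site term with ordinary standard errors: 6.1–7.3%.
- Site term with HC3 standard errors: 4.2–5.6% in all 16 settings.

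A further simulation that also tried 30 sites kept site plus HC3 at 3.5–5.7%.

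**The case against.** The strongest reply is that the excess type I error has nothing to do with ignoring site. With the metal SD 25% larger, the pooled test already runs at 6.9% when sites do not differ, and the rate falls as the site share rises. This is right. The cause is a pooled variance under 2:1 allocation with unequal SDs, and leaving site out partly masks it. The reverse case, with the single-use arm more variable, gives no inflation, and nothing in the documents says which arm varies more. A Welch test, which the plan does not rule out, stays at or below 5%. What remains is that a site term with ordinary standard errors would remove the masking, so the remedy has to address both parts.

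The second reply is that the effect is small and conditional. At shares of 5–10% the power loss is about 1–3 points. Power drops below 80% only if 8.66 is a within-site SD and the site share exceeds about 18%, and the documents establish neither. The 14% margin is meant for uncertain effect sizes, and since effect size is the difference divided by the SD, an SD larger than planned is arguably part of what it covers. All of this stands. It limits the weight of the point but does not remove the omission.

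HC3 is also one choice among several; a stratified comparison with variances estimated by arm would serve as well.

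**Conclusion.** The concern holds, as a free improvement. Site is a randomization stratum and no analysis in section 4 uses it. If sites differ and arm variances are similar, the planned test is conservative (type I error 4.4% down to 1.9% over assumed shares of 5–30%) and gives up power: about 1 to 6 points if the planning SD is total, and about 1 to 11 points if it is within-site.

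The treatment estimate is essentially unbiased and N=342 is not invalidated. If 8.66 is a total SD, the 80% target is met either way. The omission is certain from the text. Its size is not, because it rests on an assumed site share and, for any excess false positives, on a pooled test with a more variable metal arm.

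**What to change.** In section 4.1, specify for each continuous endpoint compared between arms a linear model with treatment and site as fixed effects and HC3 standard errors, reporting the adjusted mean difference with its 95% confidence interval. State both parts, since a site term with ordinary standard errors would still give too many false positives if the metal arm is more variable. For binary outcomes compared between arms, specify a Mantel-Haenszel comparison stratified by site. Keep the cutting-block success rate descriptive within Group A.

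The cost is one or two SAP sentences. No patients or data are added, and randomization already runs by site. The model spends one degree of freedom per additional site, for example 9 of 340 with an assumed 10 sites.

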#### Visit 1: Baseline (-1 to -90 days prior to surgery)

The baseline visit will occur to screen subjects, confirm study eligibility, complete the informed consent process, and enroll and randomize the subject.

- Informed consent
- Randomize patients meeting inclusion/exclusion criteria
- Collect demographics data, pre-operative knee history/diagnosis and employment status
- Visual Analog Scale (VAS) for knee pain
- Long standing AP and lateral x-rays to assess pre-operative mechanical axis alignment and posterior tibial slope. X-rays obtained within 6 months prior to surgery are acceptable for the baseline visit. The investigator may repeat x-rays if needed for clinical or imaging quality reasons.
- Complete CT scan or MRI for pre-operative planning and selection of cutting blocks (Group A Only)

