**WITHDRAWAL**

Consent to participate in this study is completely voluntary. Consent may be withdrawn at any time, if desired by the study participant or the investigator may choose to discontinue the subject. Reasons for discontinuation of a patient from the clinical study may be (1) insufficient cooperation of the patient (non-compliance); (2) technical or administrative reasons (e.g., change of investigator or move of patient or cancelled/postponed surgery outside of window); or (3) death. To formally withdraw consent to participate in this study, the participant will need to notify their treating physician.

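### Investigators who know the arm may exclude patients after randomization for unlimited reasons, and no as-randomized analysis set keeps those patients in the time comparisons

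*Combined protocol and SAP*

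**What the plan says.** Section 3.2.2 (Randomization) states: "In case the investigator decides not to include the patient after randomization, this patient will be treated as withdrawn". It sets no list of reasons and no deadline. It adds two safeguards: "The reason for withdrawal must be documented in the patient file", and "The used randomization number cannot be used again".

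The Withdrawal section says that "the investigator may choose to discontinue the subject". Its reasons (non-compliance, technical or administrative causes including surgery cancelled or postponed out of window, and death) are offered as possibilities, not as a closed list.

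Randomization takes place at Visit 1, between 90 days and 1 day before surgery (section 3.4). After allocation, section 3.2 says, "subjects randomized to Group A (Efficiency/MyKnee®) will undergo a pre-operative CT scan or MRI as standard of care", and "The investigator will perform appropriate pre-operative planning which enables the custom manufacturing of the MyKnee® cutting blocks". Group B has whatever planning imaging the investigator regards as standard.

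Section 4.1 plans a separate two-sample t-test at 0.05 for each time endpoint. It names no analysis set and gives no rule for withdrawn patients or missing times. Among the secondary objectives, section 1.3 counts the cases in which "the surgeon did not need to abort the use of MyKnee intra-operatively and default to the use of standard cutting blocks".

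**The concern.** Randomization protects the comparison only if the patients compared are those who were allocated. Here the person who decides on exclusion knows the arm. No blinding is described, and the investigator who plans custom cutting blocks cannot be unaware of the assignment. New information also arises unequally: only Group A has protocol-specified three-dimensional imaging after allocation, so reasons to drop a patient can surface more often in that arm.

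A patient excluded before surgery has no operative times under the study, and nothing requires timing a patient who is excluded but operated on anyway. If expected difficult cases leave Group A more often than Group B, the Group A mean falls for reasons unrelated to the instruments. That would favour the sponsor's single-use product and carry into the cost analysis built on the time differences. The 42 patients above the minimum of 300 replace lost numbers; they do not restore comparability.

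**Working it through.** **Inputs from the documents.** Allocation 228:114 (sections 3 and 4.2). Level 0.05 per endpoint (4.1), taken as two-sided because the null is no difference. From the table in 4.2: set-up time difference 2.985 min, SD 8.66, effect size 0.345; surgical episode time difference 5.893 min, SD 16.79, effect size 0.351.

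**Assumptions, because the documents give no exclusion rate.** A share q of Group A is dropped, and none of Group B. Patients are dropped from the top of a judged-difficulty score that correlates ρ with the measured time. Times are normal and there is no true difference. I take q = 5%, 10% and 12.3% (the last is 42/342, the planned excess over 300) and ρ = 0.3 to 0.5, with ρ = 1 as the extreme.

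**The plan's own figure.** For set-up time, the endpoint that drives N, with 2:1 allocation and 80% power:

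n(control) = (1 + 1/2) × (1.960 + 0.842)² × (8.66/2.985)² = 1.5 × 7.85 × 8.42 ≈ 99.1, rounded up to 100.

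The total is 300, and 300 × 1.14 = 342. Both match section 4.2. With 228:114, power for set-up time is 85.2%.

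**Formulas for the bias.** Let c be the (1−q) normal quantile and λ = φ(c)/(1−q).

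- Shift in the Group A mean = ρλ, in SD units.
- Variance of the retained Group A times: v = 1 − ρ²(cλ + λ²).
- SE = √(v/n_A + 1/114), with n_A the number retained.
- Type I error = Φ(−1.960 + shift/SE) + Φ(−1.960 − shift/SE).

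**Worked case, q = 5% and ρ = 0.5.**

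- c = 1.645 and λ = 0.1031/0.95 = 0.1086.
- Shift = 0.5 × 0.1086 = 0.054 SD, which is 0.054 × 16.79 ≈ 0.91 min of surgical episode time.
- v = 1 − 0.25 × (0.1786 + 0.0118) = 0.952.
- SE = √(0.952/217 + 1/114) = 0.1147, so shift/SE = 0.473.
- Type I error = Φ(−1.487) + Φ(−2.433) ≈ 0.076.

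**All cases.** The last column is from 20,000 simulated t-tests per scenario.

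| Dropped from Group A | ρ | Shift (SD) | Set-up (min) | Surgical episode (min) | Type I error, formula | Type I error, simulated |
|---|---|---|---|---|---|---|
| none | – | 0 | 0 | 0 | 5.0% | 4.9% |
| 11 (5%) | 0.3 | 0.033 | 0.28 | 0.55 | 5.9% | 5.9% |
| 11 (5%) | 0.5 | 0.054 | 0.47 | 0.91 | 7.6% | 7.4% |
| 23 (10%) | 0.3 | 0.058 | 0.51 | 0.98 | 7.9% | 8.3% |
| 23 (10%) | 0.5 | 0.097 | 0.84 | 1.64 | 13.5% | 14.8% |
| 28 (12.3%) | 0.3 | 0.070 | 0.60 | 1.17 | 9.2% | 9.2% |
| 28 (12.3%) | 0.5 | 0.116 | 1.00 | 1.95 | 17.1% | 17.8% |
| 11 (5%), exactly the longest | 1 | 0.109 | 0.94 | 1.82 | 16.3% | 17.7% |

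Relative to the planned surgical episode effect of 0.351, the 5% shifts are 9% (0.033/0.351) to 15% (0.054/0.351), and the 10% shifts are 17% to 28%. With 10% dropped at ρ = 0.5, 14.4 of the 14.8 percentage points of rejections favour Group A.

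**Which endpoints.** Patient OR time, skin-to-skin time, resection times and tourniquet time (section 3.3) depend directly on case difficulty. Set-up, transport, cleaning and sterilization depend mainly on the instrument set, and on the patient only through complexity or extra trays. The same ρ is therefore less plausible for the set-up column.

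**The case against.** The strongest reply is that the rule has legitimate uses, that the plan leaves a trail, and that the bias is only hypothetical. Much of this stands, and it rules out several stronger readings.

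- A reader might infer that the rule serves no eligibility purpose, because section 3.1 requires eligibility review before randomization. The documents do not support that. Pregnancy is an exclusion criterion, but the test is scheduled at the operative visit (3.1.2, 3.4). Baseline x-rays may also be repeated. Some arm-neutral exclusions after randomization are unavoidable. The defect is that the reasons are not limited to these.
- A reader might infer that timings of aborted MyKnee cases are lost. They are not. Falling back to standard blocks during surgery is not a decision to leave a patient out of the study; section 3.2 records timings, section 3.5 requires case report forms for all subjects, and section 1.3 counts these cases. What is missing is only a statement of the arm in which they are analysed.
- A reader might infer that the plan orders withdrawn patients out of the analysis. It does not say so. The loss follows because a patient dropped before surgery has no times and no rule retains those who are operated on.
- A reader might take about 18% as the expected error rate with 5% dropped. That requires the investigator to foresee exactly the 11 longest cases, in one arm only.

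The eligibility limits on BMI, deformity and retained hardware already narrow the range of difficulty. The documented reason, the retired number and the deviation log (3.2.3) make selective exclusion detectable. None of these prevents it, and no comparison of withdrawals by arm is planned.

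**Conclusion.** The concern holds in a limited form. Two sections give an investigator who knows the arm open discretion to remove randomized patients before surgery, and the analysis section does not define an as-randomized set. Nothing shows that selective exclusion has occurred or is intended.

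The likely size is modest if exclusions are few: about 6-8% type I error instead of 5% when 5% of Group A is dropped at a correlation of 0.3 to 0.5, and about 8-15% when 10% is dropped. The extreme 5% case gives about 18%. These figures rest on assumed rates and correlations, normal times and one-sided exclusion. Equal, arm-neutral exclusion would not bias the comparison. The exposure is mainly in intra-operative times. The point does not invalidate the design, but it is worth an amendment because the remedy is cheap.

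**What to change.** **Section 3.2.2 and the Withdrawal section.** Confirm before randomization every eligibility criterion that can be assessed then. Limit later exclusion from the study to a closed, arm-neutral list: consent withdrawn, no surgery performed, or failure of an eligibility test scheduled after randomization. Both sections must change; amending only 3.2.2 leaves the second discretion open.

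**Data collection.** Record timings for every randomized patient who has the knee replacement and has not withdrawn consent, whichever instruments were used. Reconcile this with the out-of-window surgery reason in the Withdrawal section, which as written could remove a patient who is later operated on.

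**Section 4.1.** Make the as-randomized comparison primary, and state that aborted MyKnee cases are analysed in Group A. Report post-randomization withdrawals and their reasons by arm, since patients who never have surgery contribute no times and imbalance there would remain the visible warning. An as-treated analysis may serve as a sensitivity analysis.

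**Cost.** Wording in three places, a few more timing records, and slight dilution of the contrast where MyKnee was aborted or the assigned instruments were not used. N stays 342.
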